## 9.3 Machine learning analyses

Machine learning (ML) is a specialized branch of statistics that creates updatable algorithms, which learn from evolving data in real time. This project will make use of a specially designed algorithm-building platform, that will help clinicians explore and visualize patterns in the data collected by ePOCT+ to date. Two main types of ML methods will be used: 1) supervised classification and correlation and 2) anomaly detection. The former aims to create algorithms that predict the value of a labeled feature (e.g. the result of a malaria rapid test) using alternative data. Anomaly detection, on the other hand aims to find unusual clusters of values for a certain place, time, or person, and are the basis of outbreak detection and discovering erroneous data inputs that could be used to train field workers. These analytical techniques will be used in latter stages of the project when enough data has been collected to train the ML algorithms. Within the timeframe of the project, the analyses will be done by EPFL while identifying in-country partners and capacitating them to take on ML analyses in the future.

### 9.3.1 Supervised classification and correlation

Using the insights gleaned from visualizing the data, the expert clinician group will lead the generation of clinically supervised modifications to the static algorithms in ePOCT+ that aim to 1) reduce resource consumption (e.g. predicting the results of expensive or unavailable diagnostic tests), 2) improve or

personalize diagnostic accuracy (e.g. creating algorithms adapted to local epidemiology, or better identifying patients who had severe outcomes in phase 1 or 3) improve the completeness of data collected by asking questions that would better predict the values that are missing. For this, the algorithm building platform will allow clinicians to explore various predictive methods, ranging from logistic regression, neural networks and random forests. They will control the inputs required to make the prediction and decide at what threshold the predicted result will impact care decisions. The algorithm will then be updated with accumulating data to best reflect its dynamic environment.

### 9.3.2 Anomaly detection

Various methods allow us to identify and visualize clusters of abnormal data, by highlighting these instances, clinicians and epidemiologists can train the algorithms by labeling which are of interest and what, if any, actions should be taken when they are detected. Various methods will be explored for this aim and adapted to the type of anomaly under investigation (for example unsupervised density-based approaches such as isolation forests, and k-nearest neighbors [KNN] or multidimensional non-linear kernel-based techniques such as self-organizing maps [SOM] and support vector clustering [SVC]). The clusters deemed interesting will then be investigated for gold-standard labeling by clinicians and the surveillance team and visualizations may be exported to users of the tool for training purposes (medAL-outbreak).

## 9.4 Analyses of data from mixed-methods studies

Quantitative data from cross-sectional quality of care surveys, provider clinical competency or knowledge assessments, and caregiver and patient interviews will be analyzed using conventional statistical methods to compare means (t-tests or paired t-tests) or frequencies (chi-square tests) across intervention groups or time periods. Regression analysis may also be used to explore associations of multiple predictors with outcomes of interest.

Qualitative interviews and focus group discussions will be audio-recorded and detailed notes will be taken. Records will be manually transcribed in their original language and translated into English. A qualitative data analysis software (e.g. Dedoose, Nvivo, ATLAS.ti) will be used to code the English interview transcripts in order to identify emerging themes. A predefined list of codes based on the interview guide and the recurrent themes highlighted in the detailed notes will be used. New codes will be created when new themes are identified during more detailed analysis of the transcripts. Deductive coding will be used to extract the themes based on the interview guide, but inductive coding will also be used to extract any unexpected themes that arise during the interviews.

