--	---

	
 
- Carbon footprint of the intervention or carbon-saving due to the intervention
 

Procedures and measurements	
Objective 1: Improve integrated management of sick children
 
In Phase 1, eligible HFs will be grouped into three implementation blocks of 10-12 health facilities (half intervention and half control). Randomization will not be done for reasons of feasibility and high chance of contamination if control and intervention facilities are mixed and in close proximity to each other as randomized. Therefore, boundaries between groups of intervention and control facilities will be delineated geographically.
 
Sick children will be enrolled throughout Phase 1, as new blocks of facilities are introduced every four months and control facilities are converted into intervention facilities. Children enrolled in intervention facilities will be managed using ePOCT+, with all data associated with the consultation being captured electronically. Children enrolled in control facilities will be assessed, diagnosed and treated as per routine protocols by clinicians. A similar but simplified tablet or PC application will also be used in control facilities to record only outcome measure related data using an electronic case report form.
 
Primary outcome measure: For measuring antibiotics prescribed at initial consultation, the treatment data recorded in the tablets or PCs by HWs throughout the study will be compared between intervention and control facilities, captured electronically in both facility types.
 
Secondary outcome measure: For assessing clinical cure at day 7, a simple questionnaire (asking if the child is still sick, was hospitalized secondarily, or died) will be administered to all caregivers by phone.
 
In Phase 2, all HFs will be using ePOCT+. Indicators monitored over time and space will be measured the same way as in Phase 1, except that clinical cure, secondary hospitalizations and deaths may not be collected or will be assessed through an automated phone call or SMS sent to caregivers using the same simple questionnaire (resource dependent).
 
Secondary analyses will be used to assess differences in the quality of the consultation made by HWs, including the rational use of antimicrobials (antibiotics and antimalarials). Two sources of data will be used and compared between intervention and control facilities:
 
 
- the final decision on referral, tests performed, final diagnoses retained and treatment prescribed will be recorded in the tablets or PCs by HWs at initial consultations and re-attendance visits.
 
- during a cross-sectional quality of care survey, observers in the consultation room will record key symptoms and signs assessed by HWs, diagnostic tests requested, final decision on referral, final diagnoses retained and treatment prescribed.
 
 
Objective 2: Improve the algorithm and adapt it to spatiotemporal variations
 
In Phase 2 of the study, the algorithm will be improved in terms of diagnostic and prognostic accuracy and adapted to local fluctuations in epidemiology, demography, geography and resource availability. Each potential modification will first be evaluated by the Rwandan clinical expert group for its clinical coherence, safety and potential benefit, and then applied to the retrospective data. If these analyses confirm a clinically relevant positive impact, the change in the algorithm will be implemented in all relevant locations/patient sub-groups and monitored based on the indicators relevant to the specific change in the algorithm collected throughout the study through the tablets.
 
Objective 3: Enhance M&E and supportive supervision
 
Patient-level data will also enhance M&E activities and supportive supervision of the HWs through the medAL-monitor/medAL-outbreak platform. Clinicians will use data generated from their own consultations to self-audit their clinical practices by monitoring quality of care indicators in the medAL-monitor dashboards and improve their skills in specific areas using the e-learning platform. Similarly, members of the DHMT will use medAL-monitor to identify and provide support to HFs in need of additional training and mentorship. In time, this enhanced ability to capacitate HWs and

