## 2 STUDY OBJECTIVES AND THEORY OF CHANGE

The **goal** of this study is to mitigate AMR using a novel dynamic ePOCT+ tool that helps front-line HWs manage sick patients, enhanced by additional digital platforms to promote uptake, sustainability, and integration of the tool into the health system. More specifically, this study seeks to:

### 2.1 Objective 1

**Improve the integrated management of children with an acute illness** (more specific and diverse diagnoses; reduced antibiotic prescriptions) through the provision of an electronic CDSA (ePOCT+) to clinicians working at primary care level.

*Hypothesis 1:* The use of ePOCT+ in the outpatient PHC setting in Rwanda will result in decreased prescription of antibiotics while maintaining similar clinical outcomes.

*Hypothesis 2:* The use of ePOCT+ in the outpatient PHC setting in Rwanda will result in improved quality of care.

### 2.2 Objective 2

**Improve the diagnostic and prognostic accuracy of the clinical algorithm across spatiotemporal variations in epidemiology and resources** through machine learning analyses of the data generated through the ePOCT+ tool, checked by clinical experts.

*Hypothesis 3:* Modifications in the electronic CDSA based on the results of ML analyses will enable similar or better outcomes over the course of the study despite temporal and spatial variability in disease patterns and/or availability of resources.

### 2.3 Objective 3

**Enhance the health management information system for monitoring and evaluation and supportive supervision** (increased number of meaningful indicators that are reviewed and actioned regularly) through additional data analysis and visualization of patient-level data generated by the ePOCT+ tool.

*Hypothesis 4:* The patient-level clinical data that is visualized and analyzed in near real-time will lead to improved ability of the DHMT to monitor the quality of patient care and undertake targeted supportive supervision of HFs and HWs.

*Hypothesis 5:* The patient-level clinical data that is visualized and analyzed in near real-time will lead to a more accurate epidemiological profile of the district and improved spatial and temporal resource allocation.

### 2.4 Objective 4

[figure not shown]
**Create a framework for the implementation of dynamic clinical decision support algorithms and supporting tools**, for large-scale, sustainable, and clinically responsible use of machine learning and data science in digital health.

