### 4.2.2 Cross-sectional quality of care survey

Cross-sectional surveys will be conducted to assess changes in the quality of care over time, from the baseline through the implementation of ePOCT+. Two main rounds of the survey will be conducted spaced approximately 20 months apart: prior to the intervention and during Phase 2. To account for the sequential start of the three parallel cluster studies, three additional smaller rounds of the survey will be conducted to constitute a third full round of the survey and to systematically compare quality of care between intervention and control facilities. Timing of the cross-sectional survey is marked by "x" in **Figure 6**. The surveys will be conducted in a subset (n=18) of randomly selected HFs to assess the quality of the consultation done by HWs and their level of compliance to the algorithm (and thus to guidelines). Clinical research assistants will attend and observe (without interfering) 25 consecutive consultations with children enrolled into the study per HF, thus a total of 450 HW/child pairs per round. Concurrently, client exit surveys will be conducted at the end of the consultation (linked to the observation data) to evaluate the caregiver's perception of the health care the child received. The questionnaire for this survey is adapted from the Service Provision Assessment (SPA) sick child client exit interviews (USAID et al. The Demographic and Health Surveys Program), a methodology recommended by the WHO. The modified tools used in the study can be found in **Appendix B** (B2, B3).

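### Protocol 9.4 plans t-tests and chi-square tests for the quality-of-care survey with no allowance for facility clustering; at the protocol's own ICC the between-arm type I error is about 12%, not 5%

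*Protocol*

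**What the plan says.** Protocol 4.2.2 describes a two-stage sample. "The surveys will be conducted in a subset (n=18) of randomly selected HFs", and in each of these facilities research assistants watch "25 consecutive consultations with children enrolled into the study per HF, thus a total of 450 HW/child pairs per round". Caregiver exit interviews are linked to the same consultations. There are two main rounds, one before the intervention and one in Phase 2. Three smaller rounds together form a third full round, one purpose of which is "to systematically compare quality of care between intervention and control facilities".

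Protocol 9.4 gives the analysis of the survey data: conventional methods to "compare means (t-tests or paired t-tests) or frequencies (chi-square tests) across intervention groups or time periods". It adds that "Regression analysis may also be used to explore associations of multiple predictors with outcomes of interest". Neither section mentions clustering, an ICC or a design effect for the survey.

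The survey bears on Hypothesis 2 in Protocol 2.1: "The use of ePOCT+ in the outpatient PHC setting in Rwanda will result in improved quality of care". It supplies indicators listed in Protocol 7.1, such as the share of key symptoms and signs that health workers check.

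The trial's own outcomes are handled differently. Protocol 9.1 and SAP 3.3 allow for an ICC of 0.025 in the sample size, and SAP 6.1 fits a random effects logistic model with facility as a random effect. The SAP says nothing about the survey.

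**The concern.** Consultations in one facility share staff, equipment and local habits. SAP 3.1 says as much when it notes that the facility context shapes health workers' practice. A t-test or chi-square test on 450 consultations takes its standard error from the number of consultations, whereas a between-arm difference also varies with which facilities fall in each arm. The standard error is then too small and chance differences between facilities can be reported as effects of ePOCT+.

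This matters because tablet data cannot replace the survey for every indicator. Under Protocol 8.1.6, control tablets hold only registration and an abbreviated end-of-consultation module. SAP 5.4 says clinical signs are not systematically collected, and the analysis of signs assessed in SAP 6.2 is limited to the intervention arm. For symptoms and signs checked, the observed consultations are the only planned source for comparing the arms.

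**Working it through.** **1. The plan's own figures.** Survey size: 18 × 25 = 450 per round, as stated. Main trial (SAP 3.3: 35% vs 26%, two-sided 0.05, 80% power, cluster size 660, ICC 0.025): 410 children per arm without clustering; design effect 1 + 659 × 0.025 = 17.475; 410 × 17.475 / 660 = 10.86, rounded up to the stated 11 clusters per arm. Without the design effect, 410 / 660 = 0.62, or one cluster. The sponsor therefore relies on clustering by facility for the main trial.

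**2. Inputs for the survey.** Cluster size 25 and 18 facilities come from Protocol 4.2.2. The split between arms and the significance level are not stated; I assume 9 vs 9 and two-sided 5%. The only ICC in the documents is 0.025, for antibiotic prescription; the other ICCs below are assumptions.

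**3. Between-arm comparison.** Design effect DE = 1 + (25 − 1) × ICC. Type I error of the unadjusted test = 2 × [1 − Φ(1.96 / √DE)]. The nominal sample per arm is 9 × 25 = 225, and the effective sample is 225 / DE.

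| ICC | Basis | DE | Type I error | Effective n per arm |
|---|---|---|---|---|
| 0.01 | assumed | 1.24 | 7.8% | 181 |
| 0.025 | protocol, antibiotic prescription | 1.60 | 12.1% | 141 |
| 0.05 | assumed | 2.20 | 18.6% | 102 |
| 0.10 | assumed | 3.40 | 28.8% | 66 |
| 0.20 | assumed | 5.80 | 41.6% | 39 |

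For ICC 0.025: 1.96 / √1.6 = 1.55, which gives 12.1%.

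**4. Simulation check** (9 vs 9 facilities of 25, no true effect). For ICC 0.025 and 0.20, the chi-square test on beta-binomial data rejects in 12–13% and 42% of runs; with continuity correction, 10–11% and 39–40%. The t-test on normal data rejects in 12% and 41%. A t-test on facility means (16 degrees of freedom) rejects in 4.8–5.0% at ICCs of 0.025, 0.05, 0.10 and 0.20.

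**5. Comparison over time.** If two rounds visit the same facilities and c is the correlation of the facility effects between rounds (assumed), an unpaired test has DE = 1 + 24 × ICC − 25 × ICC × c. Type I error:

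| ICC | c = 0 | c = 0.5 | c = 0.8 | c = 1 |
|---|---|---|---|---|
| 0.025 | 12.1% | 8.4% | 6.2% | 4.7% |
| 0.10 | 28.8% | 18.1% | 9.8% | 3.9% |
| 0.20 | 41.6% | 28.1% | 14.4% | 2.8% |

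The inflation shrinks as c rises, and with perfect correlation the test is conservative.

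**The case against.** Several points on the other side have force.

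- **The unit of analysis is not named.** A t-test on facility means would be sound, and 9.4 does not exclude one. But it does not call for one either, a chi-square test of frequencies ordinarily counts consultations, and the size is given as 450 pairs. The regression that might carry a facility term is optional and exploratory, and no such term is named.
- **The size is uncertain.** The 12% borrows an ICC set for a different outcome, and a lower ICC gives less. A reader might infer that observed care clusters more strongly than prescribing, and so that the rate is 12% to 42%. That is plausible, but no ICC for the survey is given, and 42% needs an ICC of about 0.20 that appears nowhere in the documents.
- **Not every comparison in 9.4 is affected alike.** A reader might apply the between-arm figures to comparisons between rounds. Step 5 shows they do not carry over if facilities are revisited, and the protocol does not say whether they are.
- **Hypothesis 2 does not rest on this survey alone.** A reader might take these figures as the false-positive rate for Hypothesis 2. The documents name no test, endpoint or significance level for it. The Synopsis also states that "Two sources of data will be used and compared between intervention and control facilities", the other source being tablet records, and SAP 6.1 models the binary secondary outcomes, including the malaria indicators, with a facility random effect.

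These points limit the size and reach of the problem. None of them supplies the missing allowance for clustering.

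**Conclusion.** The survey analysis in Protocol 9.4 is wrong as written for comparisons between arms. At the one ICC in the documents, the true standard error is √1.6 = 1.26 times the one the test would use, and a nominal 5% test rejects about 12% of the time. The rate is about 8% at an assumed ICC of 0.01, 29% at 0.10 and 42% at 0.20. These figures rest on a two-sided 5% level, nine facilities per arm and an ICC not estimated for the survey's indicators. That the error is inflated depends only on an ICC above zero, which the sponsor assumes for the same type of facility.

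The effect is confined to survey indicators. These inform Hypothesis 2 but are not its only evidence. The primary outcome and the SAP's secondary outcomes are not touched. The point should be corrected, but it does not threaten the trial's main conclusion.

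**What to change.** In Protocol 9.4 or the SAP, replace consultation-level t-tests and chi-square tests for the quality-of-care survey with one of these:

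- t-tests on facility-level summaries with facility-based degrees of freedom, paired by facility for comparisons over time if the same facilities are revisited; or
- a mixed model, logistic or linear, with a facility random effect and a small-sample correction for 18 clusters.

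Under either option, limit the arm contrast to rounds that have concurrent control facilities. The Synopsis says all facilities use ePOCT+ in Phase 2, so that round has none. State whether the same 18 facilities are revisited, how they divide between arms, and what ICC is assumed for the survey.

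This takes a few lines of text and no new data. The cost is wider intervals: by a factor of about 1.26 at ICC 0.025, and more if clustering is stronger.

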## 9.5 Estimated number of beneficiaries

Throughout the study, we expect that an average of 212 children per month per HF will be managed using ePOCT+. In Phase 1, the number of direct beneficiaries include children attended to using ePOCT+ (n=24,000) and HWs using ePOCT+ (n=120) for a total of 24,120 people. Indirect beneficiaries may include caregivers and immediate family members who are less exposed to infectious diseases as a result of better cure rates of their child/sibling. Using an average rural household size of 4.3 people according to the 2012 Census, the number of expected indirect beneficiaries is approximately 151,368 (i.e. 3\*50,456, excluding the sick child who is a direct beneficiary). The actual number is likely to be lower due to the possibility of multiple visits per child over the course of Phase 1.

In Phase 2, we expect a maximum of around 48,000 consultations over 6-7 months. The number of direct beneficiaries will be less than this estimate, because children may come to the facility more than once, either for the same illness or a different illness over the course of the study. In Phase 2, approximately 200 HWs are expected to directly benefit from using ePOCT+ and their clinical decision support and e-learning functions. Additionally, approximately 10 users of medAL-monitor/medAL-outbreak at the district and national levels will also benefit directly. Lastly, all individuals who are

capacitated IT systems management, ML, adaptation of the algorithm through medAL-creator, etc. will be included as direct beneficiaries (n=50). Because of high coverage of the intervention in Phase 2, indirect beneficiaries will be the entire population of the intervention districts (n=783,000) as a result of 1) less exposure to infectious diseases due to better cure rates of sick children; 2) reduced drug pressure and likelihood of antibiotic resistance due to reduced antibiotic prescriptions; and 3) reduced risk of illness due to more effective outbreak detection and response.

## 10 INFORMATION TECHNOLOGY, DATA MANAGEMENT AND MONITORING

### 10.1 Overall IT solution

The overall IT solution is provided by several components; some of them have been already discussed or presented previously, the diagram (**Figure 11**) below is the complete overview of the solution. From left to right we have the following components:

**medAL-creator (Medical Algorithm Creator):** The clinical algorithm management system that will allow to manage, reference, modify and deploy the different versions of the algorithm into a mobile device. medAL-creator is hosted in Switzerland and managed by the Unisanté IT team.

[figure not shown]
**medAL-reader (Medical Algorithm Reader):** The application (tablet or PC) that will contain the algorithm and be used for data acquisition by the HW. medAL-reader could be deployed in a standalone or multi-device mode. In a standalone mode the application will receive updates of the algorithm directly from medAL-creator.

**medAL-hub:** The component that enables ePOCT+ to work in a multi-device environment. It plays a role of a central database at the HF level. This component will receive the updates of the algorithm from medAL-creator and pass them on to medAL-reader (i.e. the tablets). It will also collect the data from medAL-reader and push it to medAL-data.

**Data Management System:** this component will be considered as the data hub of our solution. It will be hosted on a server in a secure data center in Kigali:

[figure not shown]
- medAL-data: This is the data collector for the country, it plays several roles:
  - o Data collector
  - o Data manager (Clean, Quality Check, Audit trail, Anonymization)
  - o Data publisher
  - o Data monitoring
- medAL-monitor/medAL-outbreak: Targeted supervision to HFs by the DHMT will be organized based on the quality of care indicators calculated in real time from the uploaded data and made available through a web-based dashboard

**Research Database:** This is a database only with anonymized data where the machine learning team will do their analyses. This database may be hosted in Switzerland where ML analyses will be performed by the EPFL team, but overtime can be done on the medAL-data server in Rwanda.

